6.3.1. Instructions for Missed Dose(s)

Subjects should be instructed that if they forget to take a dose, they can take the dose within 8 hours of the normal dosing time; otherwise, they should take their next dose at the regular time on the following day. If the subject vomits the tablets, he/she should be instructed not to take additional tablets on the same day but to take the next dose at the regular time on the following day.

Subjects who do not take the study treatment for ≥ 2 consecutive days within the first week of either treatment period (ie, Week 1 [Double-Blind Treatment Period] or Week 24 [Extension Treatment Period]) or for ≥ 7 consecutive days after the first week of either treatment period must be instructed to contact the Investigator to discuss treatment re-initiation under direct supervision and are required to return to the study site at the time they take their next dose of study treatment. The subject must take the next dose of study treatment at the study site, and cardiac monitoring should be performed as outlined in Section 10.6.7.4.

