6.3.2. Dose Interruptions

Temporary withholding of study treatment, if deemed necessary by the Investigator, is permitted for up to 6 days (after Week 1) without obtaining prior approval from the Medical Monitor. If ≥ 7 days of study treatment interruption is required for a medical reason, the Investigator must contact the Medical Monitor as soon as this is anticipated.

The instruction for missed dose(s) is outlined in Section 6.3.1.

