9.4. Extension Treatment Period

9.4.1. Week 24 Visit

The Week 24 visit will be used to assess eligibility for the Extension Treatment Period and is considered the beginning of the Extension Treatment Period. During this visit, eligibility for

entry into the Extension Treatment Period will be confirmed (ie, meets eligibility criteria; Section 4.3).

At the Week 24 visit, vital signs should be measured first, followed by ECG, predose PK sample collection, study drug dosing at the study site, and first-dose cardiac monitoring (direct observation) for at least 4 hours in all subjects continuing in the Extension Treatment Period. Cardiac monitoring is required because there is a subset of subjects who will transition from placebo in the Double-Blind Treatment Period to an etrasimod dose in the Extension Treatment Period. Refer to Section 10.6.7.4 for detailed guidance on first-dose cardiac monitoring and subject discharge criteria postdose.

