10.6.7.4. Guidance for Cardiac Monitoring Following Treatment Initiation or Re-Initiation

Cardiac monitoring following treatment initiation applies to the first dose administered in the Double-Blind Treatment Period (Day 1) and in the Extension Treatment Period (Week 24). The lowest predose HR measurement (by vital signs) will be used for comparison to the postdose measurement (by vital signs). Subjects should receive the first dose of study treatment before 12:00 PM (noon).

First-Dose Heart Rate Monitoring

Cardiac monitoring of at least 4 hours following the first dose (Day 1 and Week 24) will include the following ([Table 4](#)):

- Full baseline vital signs (HR, BP, body temperature, and respiratory rate) and 12-lead ECG will be assessed predose (ie, Baseline)
- After the first dose of study treatment (Day 1 and Week 24), subjects must remain under direct observation at the study site for at least 4 hours.
- At Hours 1, 2, and 3 (\pm 15 minutes) postdose, the HR and BP will be assessed with the subject in the seated position, with the time recorded. If the subject has an HR < 50 bpm evaluate cardiac rhythm by 12-lead ECG to identify any clinically relevant ECG changes.
- At the Hour 4 (\pm 15 minutes) discharge assessment, HR and BP will be assessed with the subject in the seated position and a 12-lead ECG in the supine position will also be performed. Subjects may be discharged from the study site after the Hour 4 assessment if they meet the discharge criteria described in [Table 5](#). Subjects not meeting the discharge criteria will require extended monitoring as described below.
- Subjects experiencing a treatment-related symptomatic event (eg, chest pain, dizziness, palpitations, lightheadedness, shortness of breath, or syncope) associated with reduction of the HR together with clinically relevant 12-lead ECG changes at any time during the 4-hour monitoring period should be discontinued from study treatment.

Table 4: Procedures to Be Performed During the Cardiac Monitoring Period

Procedure	Predose	Hours 1, 2, and 3 Postdose^a	Hour 4 Postdose^a
Blood pressure and heart rate ^b	X	X	X
12-lead ECG	X		X
Assess discharge criteria			X

^a Measurements may be taken \pm 15 minutes of the scheduled time.

^b Heart rate is based on vital signs.

ECG, electrocardiogram

Table 5: Discharge Criteria After Cardiac Monitoring

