Reversible causes of prolonged QTcF interval (eg, electrolyte abnormalities like hypokalemia and hypomagnesemia), should be corrected as clinically indicated. When evaluating a subject with new onset QTcF interval above 500 ms, referral to a physician experienced in treating cardiac conduction disorders should be considered. If treatment is interrupted, re-initiation of study treatment can only be considered if the QTcF interval is $<$ 450 ms (males) or $<$ 470 ms (females), the prolonged QTcF interval is not considered related to study treatment, the individual risk benefit is favorable (as determined by the Investigator, in agreement with the cardiologist), and after discussion with the Medical Monitor. If, after re-initiation, the QTcF interval is again prolonged above 500 ms, then study drug must be discontinued.

Cardiac Monitoring Upon Treatment Re-Initiation Following Dose Interruption

The procedure for first-dose cardiac monitoring as outlined above should be performed any time a subject misses study treatment for:

- ≥ 2 consecutive days within the first week of treatment during the Double-Blind Treatment Period or during Week 24 of the Extension Treatment Period or
- ≥ 7 consecutive days after the first week of treatment during the Double-Blind Treatment Period or after Week 24 of the Extension Treatment Period.

Subjects are not to re-initiate therapy until they return to the study site for dosing with cardiac monitoring.

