^b Subjects discontinuing prior to Week 24 should have an ET visit within 7 days of the last study treatment administration and before initiation of any new treatments. Note that safety evaluations (eg, AE query, review of concomitant medications, symptom-directed and focused physical exams as needed and relevant laboratory assessments) will be performed as described in Section 10.6.

^c Medical history will be collected during Screening and should be updated for any new conditions or medications as needed prior to dosing at the Week 0/Day 1 visit (Section 10.3.4).

^d eDiary device and training should be provided at Screening to ensure capturing of entries within the required 14-day period.

^e Study site staff will monitor subject eDiary compliance. During Screening, the completion of the following eDiary questionnaires should be monitored: DSQ (daily), FAQ (daily), PGIS (Day -8 and Day -1). At least 8 DSQ daily entries in the last 2 weeks prior to Week 0/Day 1 (Baseline) visit as well as completion of PGIS are needed for

- randomization. During the Treatment Period, the completion of the following eDiary questionnaires should be monitored: DSQ (daily), FAQ (daily), PGIS (Weeks 15, 16, 23, and 24), PGIC (Weeks 16 and 24), EoE-QOL-A (Week 0/Day 1 and Weeks 16 and 24).
- ^f Safety vital signs (resting HR and systolic and diastolic BP, body temperature, and respiratory rate) taken with subjects in the sitting position will be performed at Screening and prior to randomization on Week 0/Day 1 (Baseline). Vital signs may be repeated up to 2 times during a visit to confirm abnormal readings (no need for second reading if the first reading is normal). Inclusion and exclusion criteria related to vital signs and ECG must be reviewed and reassessed to confirm eligibility. Vital signs including HR and BP must be measured first, followed by 12-lead ECG. The 12-lead ECGs should be obtained prior to predose blood sample collection. The first-dose cardiac monitoring procedure (Section 10.6.7.4) should be repeated if a subject has a dose interruption of: 1) ≥ 2 consecutive days within the first week of treatment during the Double-Blind Treatment Period or during Week 24; or 2) ≥ 7 consecutive days after the first week of treatment during the Double-Blind Treatment Period or after Week 24.

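### Seven consecutive missed doses on Days 7–13 meet neither limb of the cardiac re-monitoring rule; its Week 24 anchor also needs clarifying for late extension entrants

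*Protocol*

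**What the plan says.** The rule for repeating supervised dosing with cardiac monitoring appears in three places in the protocol.

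- **Section 6.3.1.** The short limb is at least 2 "consecutive days within the first week of either treatment period (ie, Week 1 [Double-Blind Treatment Period] or Week 24 [Extension Treatment Period"; the long limb is at least 7 consecutive days after the first week of either period.
- **Section 10.6.7.4.** The short limb is at least 2 "consecutive days within the first week of treatment during the Double-Blind Treatment Period or during Week 24 of the Extension Treatment Period". The long limb is at least 7 "consecutive days after the first week of treatment during the Double-Blind Treatment Period or after Week 24 of the Extension Treatment Period".
- **Appendix 1, Table 7, footnote f.** The short limb applies "within the first week of treatment during the Double-Blind Treatment Period or during Week 24; or 2"; the long limb follows Section 10.6.7.4.

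None of them says how to count a gap that straddles the end of the first week.

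On the extension start, Section 9.4.1 says that the Week 24 visit "is considered the beginning of the Extension Treatment Period". Footnote a of Table 7 says only that this visit may double as extension Day 1. Footnote q provides bridging drug for subjects who enter on a later day and sets no limit on the delay. Section 10.6.7.4 opens by saying that monitoring "applies to the first dose administered in the Double-Blind Treatment Period (Day 1) and in the Extension Treatment Period (Week 24").

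Section 6.3.2 adds that temporary withholding "is permitted for up to 6 days (after Week 1) without obtaining prior approval from the Medical Monitor". It also says that if at least 7 "days of study treatment interruption is required for a medical reason, the Investigator must contact the Medical Monitor".

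**The concern.** The two limbs are meant to work together: a short gap matters early, and a longer gap matters later. A gap that crosses the boundary can fall between them. Seven missed doses in a row is the length the protocol itself treats as needing a supervised restart, yet placed on Days 7–13 it triggers nothing on a literal count.

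Section 1.2 explains why this matters: the heart-rate reduction is greatest on the first day of dosing, and re-initiation after a gap is managed like a first dose. In the Double-Blind Treatment Period the gap could arise for any subject; of about 96 planned, 96 × 6/8 = 72 are on etrasimod.

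The Week 24 wording raises a smaller question. Section 9.4.1 gives the switch from placebo to etrasimod as the reason for monitoring at extension entry. Someone who takes the first extension dose some days after the visit should have the first dosing week counted from that dose. The text does not say so in terms.

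**Working it through.** The plan gives no figure to reproduce, so the check is a count of gap patterns.

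**Inputs.** Section 9.3.1 defines Day 1 as the day of first dose, so the first week is Days 1–7. The first dose of a period is supervised, so a gap starts on day s ≥ 2 and lasts L days. The thresholds of 2 and 7 days come from the three places above.

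**Literal rule.** Let a be the missed days up to Day 7 and b the missed days after Day 7. Re-monitor if a ≥ 2 or b ≥ 7.

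**All gaps with L ≥ 7.**

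- s ≤ 6: a = 8 − s, which is at least 2, so the rule triggers.
- s ≥ 8: b = L, which is at least 7, so the rule triggers.
- s = 7: a = 1 and b = L − 1, so the rule triggers only if L ≥ 8.

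The single escape is s = 7, L = 7. Its neighbours show how isolated it is:

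| Missed days | L | a | b | Triggers? |
|---|---|---|---|---|
| 6–7 | 2 | 2 | 0 | yes |
| 6–12 | 7 | 2 | 5 | yes |
| 7–13 | 7 | 1 | 6 | **no** |
| 7–14 | 8 | 1 | 7 | yes |
| 8–14 | 7 | 0 | 7 | yes |

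In the extension, with entry on Day 169 and a first week of Days 169–175, the matching gap is Days 175–181 (1 day in, 6 after).

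**Dependence on the reading.** If the first week were taken as Days 1–8, the hole would move to Days 8–14. If a gap had to lie wholly inside one window, every gap of 7 or more days starting on Days 2–7 would escape. If a site classed a gap by its total length and the day dosing resumes, none would.

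**Week 24 anchor (illustration, not a risk estimate).** Gaps of 2–6 days lying wholly inside dosing days 2–7 of the extension number 5 + 4 + 3 + 2 + 1 = 15. If Week 24 labels the first week of extension dosing, 0 of 15 escape at any delay. Now assume instead that it means the 7 days from the visit, with the first extension dose k days later. Only dosing days 1 to w = 7 − k then count as the first week. A gap escapes if it starts on or after day w, and 7 − s gaps start on day s:

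| Delay k (days) | 0 | 1 | 2 | 3 | 4 | 5 or more |
|---|---|---|---|---|---|---|
| Escaping, of 15 | 0 | 1 | 3 | 6 | 10 | 15 |

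Example: visit on Day 169, first extension dose on Day 174, doses missed on Days 175–180. The visit week (Days 169–175) holds 1 missed day and 5 follow, so nothing triggers. Counted from the first dose, 6 of the first 7 days are missed, which triggers.

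**The case against.** On Days 7–13, the strongest reply is that this is one boundary pattern, and a sensible site would look at seven missed doses and re-monitor. There are also partial backstops. A medically required interruption of that length needs Medical Monitor contact under Section 6.3.2, and the Week 2 telehealth contact (Day 15 ± 3) must review missed doses under Section 9.7.1. These make an unnoticed gap less likely. They do not close the hole: Section 6.3.2 does not itself call for cardiac monitoring and does not reach doses the subject simply misses, and the telehealth review mandates no monitoring.

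On Week 24, the reply is stronger and largely stands. A reader might infer that the three statements conflict, or that former placebo subjects who enter late are bound to be re-dosed unmonitored. The documents do not support either inference. All three places use the same anchor. Section 6.3.1 states the governing idea as the first week of either period and offers Week 24 as the name of that week in the extension. Section 1.2, the opening and Table 5 of Section 10.6.7.4, the baseline definition in Section 11.3 and SAP Section 6.2 all attach Week 24 to the first extension dose. Section 9.4.1 requires first-dose monitoring of everyone who continues. The escape counts above zero come entirely from the visit-anchored assumption, which no section states.

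Nor does Section 6.3.2 waive re-monitoring for gaps of up to 6 days. It concerns withholding without prior approval, and it refers missed doses back to Section 6.3.1.

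**Conclusion.** The Days 7–13 hole is real on the literal text. Exactly one gap of 7 or more days per treatment period meets neither limb. This rests on counting missed days separately within each limb with a first week of Days 1–7; classing gaps by total length and resumption day would remove it.

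The Week 24 wording is a secondary ambiguity. The label reading is the better supported one and leaves no escape. The visit-anchored reading is possible only because footnotes a and q allow later entry while Section 9.4.1 starts the extension at the visit. The documents do not give the number of late entrants, and it is probably small. At most the planned placebo arm, 96 × 2/8 = 24, would be new to etrasimod, which is an upper bound and not an estimate of those affected.

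Severity is minor. Section 1.2 reports no symptomatic bradycardia on first dose and only rare, asymptomatic, transient AV block. Any extension subject concerned would already have had a supervised first extension dose. Endpoints, sample size and efficacy analyses are unaffected.

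**What to change.** Use one wording in Section 6.3.1, Section 10.6.7.4 and Table 7 footnote f. Supervised re-dosing with cardiac monitoring is required after:

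1. any gap that includes at least 2 consecutive missed days within the first 7 days counted from the first dose of that treatment period; and
2. any gap of at least 7 consecutive days, whenever it falls.

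Counting from the first dose settles the Week 24 question for any entry day. Dropping the after-the-first-week condition from the long limb closes the Days 7–13 hole.

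Compared with the label reading of the current rule, this adds one gap pattern per period and removes none. Compared with the visit-anchored reading, it also restores the late-entrant gaps tabulated above. The procedure already exists, so the cost is an edit in three places and a few more supervised re-doses.

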10.6.7.5. Pulmonary Function Monitoring

Based on changes in pulmonary function observed with the use of S1P receptor modulators such as fingolimod and siponimod, approved for relapsing multiple sclerosis [43,44], pulmonary function will be assessed in this study. PFTs will be performed at the start and conclusion of the study.

Subjects experiencing clinically significant dyspnea or other respiratory AEs, may need to have additional PFT testing as clinically indicated. Severity of respiratory AEs should be categorized using the CTCAE scale described in [Appendix 8](#). Investigators should consider interruption of study treatment when there is a clinically significant respiratory AE considered related to study drug that leads to limitations in instrumental or self-care activities of daily living (ADL). The decision to interrupt study treatment should be discussed with the Medical Monitor. Subjects should be promptly referred to a pulmonologist for further evaluation and treatment. The pulmonologist should be provided with a standard referral letter explaining the reason for the referral along with information about the investigational drug. Clinically significant respiratory AEs should be followed until there is stability, improvement, or resolution.

Re-initiation of study treatment can only be considered if the respiratory AE has improved, stabilized, and/or resolved, and is not considered related to study treatment; the individual risk-benefit is favorable (as determined by the Investigator, in agreement with the pulmonologist); and after discussion with the Medical Monitor.

10.6.7.6. Ophthalmic Symptom Monitoring

Subjects experiencing unexpected ophthalmic symptoms, including blurred vision, decreased visual acuity, or other clinically significant ocular AEs, without a known/suspected etiology may need to have repeat ophthalmoscopy and OCT testing performed.

If, during the study, there are complaints of decreased vision or identification of worsening visual acuity (equal to or more than 2 lines on a standard eye chart using best corrected vision) then an unscheduled ophthalmic examination should be performed:

- Best corrected visual acuity measurement
- Ophthalmoscopy (may include contact lens biomicroscopy to examine the macula and optic disc)
- OCT for all subjects to investigate a suspected diagnosis of macular edema

Note: For both scheduled and unscheduled visits, in case of suspected macular edema based on the ophthalmoscopy or a relevant increase of central foveal thickness, then FA may be performed.

If there is evidence of new onset macular edema considered related to study treatment, then study treatment should be interrupted as appropriate and the subject should be monitored closely with the appropriate diagnostic and clinical work-up.

Subjects with a diagnosis of macular edema considered related to study treatment during the study must interrupt the study drug. These subjects must be followed up monthly with ophthalmologic evaluations until such time as resolution is confirmed or no further improvement is expected by the ophthalmologist (based on a follow-up period of no less than 3 months).

These evaluations will include repeat best corrected- visual acuity, fundus examination, and OCT. FA may also be performed at the discretion of the ophthalmologist. If the subject does not show definite signs of improvement on examination by specialist testing (eg, OCT, FA) 6 to 8 weeks after interruption of study drug, then therapy for macular edema in conjunction with an ophthalmologist experienced in the management of this condition should be initiated.

For subjects diagnosed with macular edema, copies of the colored OCT and FA images (if conducted) should be kept by the investigative site as source documents. These documents may need to be submitted for review by an independent panel.

10.6.8. Adverse Events

10.6.8.1. Definitions

10.6.8.1.1. Adverse Event

An AE is any untoward medical occurrence that does not necessarily have a causal relationship with this treatment. An AE can therefore be any unfavorable and unintended sign, symptom, or disease temporally associated with the use of a medicinal product, whether or not considered related to the medicinal product.

AEs can include, but are not limited to, any of the following:

- Unfavorable changes in general condition
- Subjective or objective signs/symptoms
- Concomitant disease or accidents
- Clinically relevant adverse changes in laboratory parameters over the course of the study
- Pre-existing conditions that worsen in severity, increase in frequency, or have new signs/symptoms

Additional guidance on the management of AEs according to assessed severity is provided in [Appendix 9](#).

10.6.8.1.2. Serious Adverse Event

An AE should be classified as an SAE if it meets one of the following criteria:

- | | |
|-------------------|-----------------------------------------------------------------------------------------------------------------------------------------------------------------|
| Fatal: | The AE resulted in death. |
| Life-threatening: | The AE placed the subject at immediate risk of death. This classification does not apply to an AE that hypothetically might cause death if it were more severe. |

Hospitalization:	The AE required or prolonged an existing inpatient hospitalization. Hospitalizations for elective medical or surgical procedures or treatments planned before the signing of informed consent in the study or routine check-ups are not SAEs by this definition.
Disabling/ incapacitating:	The AE resulted in a persistent or significant incapacity or substantial disruption of the subject's ability to conduct normal life functions.
Congenital anomaly or birth defect:	An adverse outcome in a child or fetus of a subject exposed to the study treatment before conception or during pregnancy.
Medically significant:	The AE did not meet any of the above criteria but could have jeopardized the subject and might have required medical or surgical intervention to prevent one of the outcomes listed above or involves suspected transmission via a medicinal product of an infectious agent.

Additionally, in this study, any diagnosis of PML will be considered an SAE.

10.6.8.1.3. Adverse Drug Reaction

An adverse drug reaction (ADR) in the pre-approval clinical experience with a new medicinal product or its new usages, particularly as the therapeutic dose(s) may not be established, is any noxious and unintended response to a medicinal product related to any dose. The phrase "responses to a medicinal product" means that a causal relationship between a medicinal product and an AE is at least a reasonable possibility (ie, the relationship cannot be ruled out).

